It was chosen the product *LUTEIN ofta 0,5 gocce*, because Sooft Company proved to be able to supply this drug without any charges, also signing a statement that certifies the fact that the scientific results of the research will remain at the disposal of the scientific community and that the management of the intellectual property protection activity concerning any invention that may derive from the research is made according to the law in force and mainly to Art. 65 of the Executive Decree no. 30 from 10 February 2005 – "The Code of Industrial Property". In conclusion the results of the research will remain available for the Scientific Community and shall not be used for commercial purposes or profit.

The registration and trading status of the product participating at the study

The Registers of the Ministry of Health concerning non-pharmacological products The product is registeres in the Register of dietary supplements on the web site of the Ministry of Health (http://www.ministerosalute.it/alimenti/dietetica) and classified with the following code: 905619452, according to the executive decree no. 111 from 27 January 1992. These products are submitted to the European Directive concerning food, according to the Executive Decree no. 169 from 21/05/2004, and to the European Directive 2001/20/EC concerning drugs, transposed to Italian level throyh the executive decree 211 from 24/06/2003.

Ingredients: solution of 5% Lutein and 2,25% Zeaxanthin with excipients (Corn starch, glucose, potassium sorbate, xanthan gum, citric acid).

Description: LUTEIN ofta 0,5 gocce is a dietary supplement based on lutein and zeaxanthin.

The lutein and its isomer, zeaxanthin, are two carotenoids highly spreaded in nature, which cannot be synthetized by the human body. They are normaly absorbed through food rich in such carotenoids (vegetables with green leaves, with big leaves as turnips and spinach, and fruits such as apricots and kiwi) and through breast milk. After absorption, the lutein and zeaxanthin are distributed to all tissues, but they are selectively accumulating in the eyes. Mainly, they are focusing in the retina and macula lutea, the latter being the place where clear images are formed, whose development is complete around the 4th or 5th month of life. The lutein and zeaxanthin are the only pigments present at the level of macula lutea and have a protection role.

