They contribute and maintain the functionality and integrity of the eye's sensitive structures (retina, iris, lens), preventing or reducing the damages caused by free radicals. In specialized literature is largely described their high antioxidant

	activity and the advantages of a consumption or supplement. Lutein and zeaxanthin pass through the placental barrier, they are also present in the colostrums and breast milk and it is believed that they take part to the embryogenesis of the retina and to the development of visual functions during the first weeks of life. As a result, the lutein and zeaxanthin are essential to the health of the eye, both on adults and children suring their first hours of life. Thus, the absorption of these substances proves to be necessary in situations of necessity growth or in case of deficient intake, both during the aging period of the ocular structures responsible for the visual function (macula), and during their conservation period. The lutein and zeaxanthin do not present contraindications and can be taken at any age. Use: LUTEIN ofta 0,5 gocce is indicated in situations of necessity growth or in case of deficient food intake of its components on different age groups. LUTEIN ofta 0,5 gocce can be useful especially in preventing macular or retina damages.	
Study Objectives	Main objective	
, and a second s	To evaluate if the administration of pharmacology doses of Lutein/Zeaxanthin micronutrients in water (LUTEIN ofta 0,5 gocce – Neoox) is able to reduce the level of radicalemy and at the same time to elevate the antioxidant power of premature newborns (gestational age: \leq of 32 weeks and / or weight at birth: \leq 1500 grams).	
Study scketch	pilot study, non-commercial, with food supplement, treated vs. control with a	
	ratio 1: 1 double-blind. The identical vials, corresponding to placebo and active product, have an alphanumeric code without meaning for the operator, but that identifies the traty from control, in an anonymous document kept by the Statistical. The document will be placed in a sealed and anonymous envelopeand it will be kept open by the statistician at the time of data analysis.	
People	Inclusion criteria	
participating at	• Newborns with a weight ≤ 1.500 grams and/or gestational age ≤ 32 weeks;	
the study and their number	Male and female newborns; Newborns where reports went to sign the information forms informed.	

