Treatment and dosage	Products administered: LUTEIN ofta 0,5 gocce, containing a solution of 5% Lutein and 2,25% Zeaxanthin with excipients (Corn starch, glucose, potassium sorbate, xanthan gum, citric acid) (group A) Placebo solution with unique excipients (Demineralised water, potassium sorbate, xanthan gum, citric acid) (group B) Experimental Group: Group A (25 newborns) will be treated with LUTEIN ofta 0,5 gocce, (1 ml per Kg equal to 0,5 mg of lutein and 0,05 of zeaxantin), divided in two additional administrations during the day from the standard hospital treatment foreseen. The
	Products administered: LUTEIN ofta 0,5 gocce, containing a solution of 5% Lutein and 2,25% Zeaxanthin with excipients (Corn starch, glucose, potassium sorbate, xanthan gum, citric acid) (group A) Placebo solution with unique excipients (Demineralised water, potassium sorbate, xanthan gum, citric acid) (group B) Experimental Group: Group A (25 newborns) will be treated with LUTEIN ofta 0,5 gocce, (1 ml per Kg equal to 0,5 mg of lutein and 0,05 of zeaxantin), divided in two additional administrations during the day from the standard hospital treatment foreseen. The first dose will be given within 36 hours of life, the least to 30 th day of life. Control Group: Group B (25 newborns) treated with Placebo solution (additionaly to the standard hospital treatment foreseen. The first dose will be given within 36 hours of life,
	Products administered: LUTEIN ofta 0,5 gocce, containing a solution of 5% Lutein and 2,25% Zeaxanthin with excipients (Corn starch, glucose, potassium sorbate, xanthan gum, citric acid) (group A) Placebo solution with unique excipients (Demineralised water, potassium sorbate, xanthan gum, citric acid) (group B) Experimental Group: Group A (25 newborns) will be treated with LUTEIN ofta 0,5 gocce, (1 ml per Kg equal to 0,5 mg of lutein and 0,05 of zeaxantin), divided in two additional administrations during the day from the standard hospital treatment foreseen. The first dose will be given within 36 hours of life, the least to 30th day of life. Control Group: Group B (25 newborns) treated with Placebo solution (additionaly to the standard

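### As listed, the placebo lacks two of the active product's excipients, and identical vials do not secure blinding once the contents are taken out for dosing

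*Combined protocol and SAP*

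**What the plan says.** The active product's composition appears twice. The section on the product's registration and trading status gives "Ingredients: solution of 5% Lutein and 2,25% Zeaxanthin with excipients (Corn starch, glucose, potassium sorbate, xanthan gum, citric acid". Treatment and dosage repeats the same excipients, "with excipients (Corn starch, glucose, potassium sorbate, xanthan gum, citric acid) (group A". The same section describes the control product as "Placebo solution with unique excipients (Demineralised water, potassium sorbate, xanthan gum, citric acid".

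The Study sketch calls the trial "ratio 1: 1 double-blind" and gives the means: "The identical vials, corresponding to placebo and active product, have an alphanumeric code without meaning for the operator". The key stays in a sealed envelope with the statistician until the data are analysed, and the Randomization row assigns infants through a web system.

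Under Way of intake, the product is added to milk or to a little glucose and given by mouth or by gavage. On the actives, the product description says "The lutein and zeaxanthin are the only pigments present at the level of macula lutea", and the background credits them with absorbing blue light.

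**The concern.** A placebo should differ from the active product only in the substance under test, and staff should not be able to tell the two apart. On the face of the plan, neither condition is met with certainty.

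First, the placebo wording, most naturally read as excipients only, suggests that a vehicle-matched control was intended, but the listed contents do not match the active vehicle. Second, the masking described is that of the container and the code, while the contents have to leave the container at every dose. A solution of pigments and a solution with no listed pigment or colourant might look different at that moment.

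If staff could tell the products apart, the first things at risk would be those that depend on judgement: adverse events recorded as the doctor observes them, the assessments of ROP, NEC, IVH, BPD and infections, and discretionary care such as oxygen, ventilation, steroids and feeding. Withdrawal is also at risk, because parents may stop at any time and recruitment continues until 25 + 25 is reached. The Statistical Analysis section plans a plain Student t test and gives no rule for infants who stop treatment, so unequal care or withdrawal could carry through to TH and BAP.

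**Working it through.** The plan gives no figure to reproduce here. The check compares the texts, followed by one illustration on assumed values.

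**1. Ingredient lists side by side** (product description; Treatment and dosage)

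| Component | Active (A) | Placebo (B) |
|---|---|---|
| Lutein, zeaxanthin | listed | not listed |
| Corn starch | listed | not listed |
| Glucose | listed | not listed |
| Potassium sorbate | listed | listed |
| Xanthan gum | listed | listed |
| Citric acid | listed | listed |
| Demineralised water | not listed | listed |
| Any colourant | not listed | not listed |

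Active minus placebo = lutein, zeaxanthin, corn starch, glucose. Placebo minus active = demineralised water. The unmatched excipients are therefore 2 of the active product's 5. The active list is the same in both sections, so it is not a single slip. Water is probably not a true difference, because the main objective describes the active micronutrients as being in water.

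**2. How much the excipient difference could matter.** No amounts are given. The dosing volume for group A is 1 ml per kg, divided over two administrations. Way of intake allows milk or glucose as the carrier without restriction by arm, so group B may also receive glucose with dosing. The size of any excipient effect cannot be derived from the plan.

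**3. What the masking covers**

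- Allocation: web system.
- Key: sealed, held by the statistician.
- Container: identical, with a code that means nothing to the operator.
- Contents: nothing on colour, taste, smell, viscosity or opacity.
- Preparation: the person who prepares the dose is not named, and nothing places that person outside the care team.
- Frequency: two administrations a day for 30 days is 2 × 30 = 60 occasions per infant in group A.

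**4. What is exposed.** Evaluation Parameters names the oxidative stress biomarkers as the only efficacy measure. Laboratory results are handled centrally in Siena, which limits direct influence on TH and BAP. Siena is also one of the three recruiting centres, and the plan does not state that assay staff are blinded. Adverse events and the clinical assessments have no such protection.

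**5. Illustration with assumed bias sizes.** Suppose lutein has no effect, but the arms differ for another reason (excipients, care, withdrawal) by a fraction b of the planned effect. From Sample size: BAP effect 500, SD 466; TH effect 50, SD 64; n = 25 per arm. Alpha is taken as 0.05 two-sided, reading the printed 0.05% as a misprint. The t statistic then has 48 degrees of freedom and non-centrality λ = (b × effect / SD) × √(n/2), with √12.5 = 3.536. For BAP at b = 0.25, λ = (125/466) × 3.536 = 0.95. For TH at b = 0.25, λ = (12.5/64) × 3.536 = 0.69.

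| b (assumed) | BAP difference | Rejection rate, BAP | TH difference | Rejection rate, TH |
|---|---|---|---|---|
| 0 | 0 | 5.0% | 0 | 5.0% |
| 0.10 | 50 | 6.6% | 5 | 5.8% |
| 0.25 | 125 | 15.3% | 12.5 | 10.4% |
| 0.50 | 250 | 46.0% | 25 | 27.3% |

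The table shows how sensitive the test would be to a bias of a given size. It is not evidence that any such bias exists.

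**The case against.** The strongest reply is that the two lists may not have been compiled on the same basis. The active list names no water although the objective describes the product as in water, and the placebo wording points to an intended vehicle-only control. A transcription gap is then a live explanation. This stands, and it is why the fix begins with reconciliation. It does not remove the point, because the plan as written still describes two different vehicles.

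On blinding, "The identical vials, corresponding to placebo and active product" can be read as covering appearance as well as the container. The pigment statements concern the macula and light absorption, and no section gives the colour of the solution or says whether it would show in a vial, a syringe or milk. This also stands: a visible difference is a fair inference, not a documented fact.

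Finally, the main objective rests on laboratory measures handled centrally, allocation is by web system and the key is sealed. That limits the damage to TH and BAP, but not to the clinician-observed outcomes or to withdrawal.

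A reader might go further and infer that blinding is broken and that the arm could be identified for all 50 infants. The documents do not support this, since they do not describe the appearance of either solution or who prepares the doses. A reader might also infer that no difference could be attributed to lutein and zeaxanthin. That is too strong: nothing in the plan suggests that corn starch or glucose changes TH or BAP, the amounts are unknown, and both arms may receive milk or glucose with the dose.

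**Conclusion.** The point holds in two parts of unequal certainty. The excipient mismatch is explicit: 2 of 5 listed excipients of the active product are absent from the placebo. Its effect on TH or BAP is unknown and may be small.

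The weakness in blinding is an inference from three facts: the actives are described as pigments, the placebo lists no colourant, and only the vials are said to be identical. The correct conclusion is that blinding at dosing is not secured. The main exposure is in adverse events, the five clinical assessments, co-interventions and withdrawal; for TH and BAP it is indirect. No magnitude can be taken from the documents.

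The conclusion assumes that the ingredient lists are meant to be complete and that no unstated masking of the contents exists. If either assumption is wrong, the corresponding part becomes a matter of wording only.

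**What to change.** Before the first infant is enrolled:

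- Reconcile the two ingredient lists with the supplier and correct the protocol if one is incomplete.
- If the difference is real, either have the supplier provide a vehicle-matched placebo, or state in the protocol and the report that the contrast includes the excipients. The composition itself is for the sponsor and supplier to settle.
- In either case, dispense both products in opaque vials and opaque oral syringes, and say in the Study sketch how the contents are masked at dosing.
- State that those who assess adverse events and clinical outcomes, and those who run the TH and BAP assays, are blinded to arm.

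The cost is opaque dispensing materials for 50 infants, a few lines of protocol text and, only if the mismatch is real and matching is chosen, a placebo batch from the company that already supplies the product free of charge. The sample size and the analysis are unaffected.

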The recent Gong work has evaluated the role of lutein / zeaxanthin comparing the data obtained from various studies, including those of Romagnoli, Dani and Manzoni. Furthermore the RCT analysis of Rubin on the subject, it can be concluded that lutein / zeaxanthin are well tolerated and well absorbed from preterm infants also after oral administration.

The extremely interesting result that has emerged although not statistically significant (probably due to the small sample) is that supplementation with lutein / zeaxanthin reduced the incidence and severity of ROP.

Our protocol is born from the idea that given the interesting results of earlier work is considered important to deepen a dosage of at least 1 ml / kg equal to 0,5 mg of lutein and 0.05 mg of zeaxanthin.

It 'important to assess the value of the key markers of oxidative stress biological

antioxidant potential (BPT) and total hydroperoxide (TH) during and after treatment.

Already in a previous work (S. Perrone, M. Longini) has demonstrated a reduction in radicalemia in term infants, during and after administration of lutein / zeaxanthin by determination of the BTP and TH.

Preparation based on lutein ans zeaxanthin have never reveled on humans negative or harmful effects after administration, or to the gastrointestinal or sistemis level. In recent studies there were not reported adverse phenomena after administrating 20 mg/day of lutein or zeaxanthin for a period of 6 months, or interactions with other liposovable nutritive elements.

Justifying the noncommercial character of the study

This study is based on the administration of a dietary supplement of lutein/zeaxanthin. It is included in the category of a spontaneous/non-commercial pilot study, because it is born from the need of private healt care of identifying a natural antioxidant product which may reduce the severeness of the diseases related to the prenatal period, limiting the sufferance of newborns and their families, by reducing simultaneously the charges in SSN pregnancy which arise from the standard treatments and short-term and medium to long-term rehabilitation.

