number	• Newborns whose parents want to sign the information form – informed consent.	
	Consent	
	Exclusion criteria	
	• Informed consent is not signed	
	 Infants of birth weight ≥ 1.500 gramms and/or gestational age > 32 weeks infants hospitalized after 36 hours of life 	
	Infants with ophthalmologic disease at randomization	
	• infants with severe malformations	
	Number of nationts about to be varietaved	
	Number of patients about to be registered It is expected to register a total number of 50 newborns divided in two groups:	
	• Experimental group A: 25 newborns treated;	
	Control group B: 25 newborns treated.	
Randomization	Subsequently enrollment patients will be randomly divided into Group A and Group B throught a web system that allows the randomization into three different recruitment centers	

	T
Number of centres	Multicenter pilot study. At the study will participate three Italian experimental centres: Naples, Siena and
	Padova.
	The centre from Naples will be the national coordinator and the center from Siena
	will handle in a centralized way the laboratory results. The center from Padova
	will help to recruit an adequate number of cases.
Sample size	BAP and TH are two bio-markers with different hypothetical changes clearly different. For this reason we will use the study method proceeds by the following online site http://clincalc.com/stats/samplesize.aspx (Rosner B. Fundamentals of Biostatistics. 7th ed. Boston, MA: Brooks/Cole; 2011). The inserted reference values are for BAP 2361 (\pm 466) μ mol/L and for TH 156.75 (\pm 64.0) Ucarr (Perrone S., Longini M. et. Al). The difference for BAP that we hypothesize to find is an increase of at least 500 μ mol / L which is approximately 20% of the control data. By setting α = 0.05% and β =0.1% with a power of 90% the number of samples required is 25 + 25 = 50. For the TH assume a decrease of 50 Ucarr which is approximately 30% of the
	data of the control. By setting $\alpha = 0.05\%$ and $\beta = 0.2\%$ with a power of '80% also in this case the required number of samples is $25 + 25 = 50$.
	However $25 + 25$ is the minimum number. Taking into account any ongoing study waivers (parents may request to discontinue treatment at any time) which go beyond statistical calculations. So in case of necessity we will recruit a number of infants to reach the minimum number according to the design of the protocol (25 $+$ 25).
Treatment and	Products administered:

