Way of intake Duration of the period of administration	Products administered: LUTEIN ofta 0,5 gocce, containing a solution of 5% Lutein and 2,25% Zeaxanthin with excipients (Corn starch, glucose, potassium sorbate, xanthan gum, citric acid) (group A) Placebo solution with unique excipients (Demineralised water, potassium sorbate, xanthan gum, citric acid) (group B) Experimental Group: Group A (25 newborns) will be treated with LUTEIN ofta 0,5 gocce, (1 ml per Kg equal to 0,5 mg of lutein and 0,05 of zeaxantin), divided in two additional administrations during the day from the standard hospital treatment foreseen. The first dose will be given within 36 hours of life, the least to 30th day of life. Control Group: Group B (25 newborns) treated with Placebo solution (additionaly to the standard hospital treatment foreseen. The first dose will be given within 36 hours of life, the least to 30th day of life. The product will be administered by adding it in the milk (human or formulae), or in a small quantity of glucose, either orally or by gavage. The administration of the product (LUTEIN ofta 0,5 gocce) starts within the first 36 hours of life and continues with daily administration for 30 days.
Way of intake Duration of the period of administration	Products administered: LUTEIN ofta 0,5 gocce, containing a solution of 5% Lutein and 2,25% Zeaxanthin with excipients (Corn starch, glucose, potassium sorbate, xanthan gum, citric acid) (group A) Placebo solution with unique excipients (Demineralised water, potassium sorbate, xanthan gum, citric acid) (group B) Experimental Group: Group A (25 newborns) will be treated with LUTEIN ofta 0,5 gocce, (1 ml per Kg equal to 0,5 mg of lutein and 0,05 of zeaxantin), divided in two additional administrations during the day from the standard hospital treatment foreseen. The first dose will be given within 36 hours of life, the least to 30th day of life. Control Group: Group B (25 newborns) treated with Placebo solution (additionaly to the standard hospital treatment foreseen. The first dose will be given within 36 hours of life, the least to 30th day of life. The product will be administered by adding it in the milk (human or formulae), or in a small quantity of glucose, either orally or by gavage. The administration of the product (LUTEIN ofta 0,5 gocce) starts within the first 36 hours of life and continues with daily administration for 30 days. Duration of the observation period of the patient registered

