laboratory investigations foreseen. The second semester will be used to study and analyse the results achieved.

Procedures

Methodology:

When born, premature newborns that are comply with the inclusion parameters will be introduced and separated in two random groups (A and B).

All newborns, during the observation period, will be submitted to the blood collection (1 ml) from the umbilical cord and peripheral (at the same time with the routine collections) on which there will be performed blood gas analysis and oxidative stress markers (TH and BAP). All registered newborns will also be submitted to the verification of their history concerning the examination and collection, in view of evaluation the presence or absence of ROP, NEC, IVH, BPD and infections.

Collection Time

- T0, basic at birth, before begining the treatment: blood collection from the umbilical vein.
- T1, first check, to 15 days after initiation of treatment: peripheral blood collection in view of verifying it before the Lutein/zeaxanthin administration.
- T2, second check, at 30th day since the begining of treatment: peripheral blood collection in view of verifying it before the Lutein/zeaxanthin administration.

The parents will be informed concerning the experimental procedure and the checks schedules.

It will be required the written consent of the parents.

The protocol shall be submitted to approval to the local ethics commission.

Evaluation Parameters:

Efficiency:

a) Evaluation of oxidative stress biomarkers in the peripheral blood of the premature newborn before and after the treatment.

Tolerability:

There will be transcribed on the data sheet possible adverse events which may be observed by the doctor.

Evaluation Scale

- a) Evaluation of the oxidative stress: by deremining the oxidative stress biomarkers and registering them in the data sheet.
- b) They must be indicated:

Demographic Characteristics

- Sex
- Gestational Age
- Weight (with percentile)
- Mode of delivery
- Preeclampsia
- Premature rupture of membranes
- Using steroids before birth
- Using antibiotics before birth
- Use of drugs or harmful substance before birth

Clinical features

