	 Apgar score Use of surfactant Umbilical catheter CVC location and duration Intubation Mechanical ventilation (procedures and time) Supplementation of O2 Incidence of infections Use and type of antibiotics Use and type of antifungal Use and type of post-natal steroids Use and type inotropic Use of NPT Duration of treatment in NICU Nutritional Characteristics: Oral feeding start time Exclusive oral feeding start time Fluid volume Intake calories (protein, carbohydrates and fats) Use of maternal and /or uman milk Other therapies associated and/or permitted During the trial period it is not permitted any product administration or antioxidant activities (anti-radicals) or products which contain even a sole
Basic examination	component having this result, excepting the protocol. At birth, as it is foreseen by newborn protocols, the babies will be submitted to
	several medical examinations.
Control examination	From the Birthing Unit, the newborns will be transered to intensive care rooms where they will be submitted to multiple control examinations.
Follow-up examinations	As it is foreseen in neonatal protocols.
Statistical Analysis	The Student t test for independent data is the type of analysis that will be used to assess statistically significant differences between the parameters recorded in the two groups (treated and control). The Student t test is the method of choice for analysis as it allows to evaluate the values of a continuous random variable measured in not very many samples (25 subjects per group). It will be using the statistical package SPSS system.

REFERENCES

Lutein: description, pharmacokinetics activity and characteristics, mechanism of action, safety and tolerability

- 1. Shao, A. and Hathcock, JN. Risk assessment for the carotenoids lutein and lycopene. Regul Toxicol Pharmacol. 2006 Aug;45(3):289-98.
- 3. Khachik F, de Moura FF, Chew EY, Douglass LW, Ferris FL 3rd, Kim J, Thompson DJ. The effect of lutein and zeaxanthin supplementation on metabolites of these carotenoids in the serum of persons aged 60 or older. Invest Ophthalmol Vis Sci. 2006 Dec;47(12):5234-42.

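### The planned t test is valid but gives the T0 values of TH and BAP no role and names no main timepoint; ANCOVA of T2 on T0 is a low-cost improvement, and the endpoint wording needs reconciling with the umbilical-vein baseline

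*Combined protocol and SAP*

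**What the plan says.** The Statistical Analysis section names one method: "The Student t test for independent data is the type of analysis that will be used to assess statistically significant differences between the parameters" of the treated and control groups. It mentions no covariate, no change score and no timepoint. The main objective and the Sample size section name no timepoint either.

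Under Procedures, Collection Time, the baseline is "T0, basic at birth, before begining the treatment: blood collection from the umbilical vein". T1 is a peripheral sample 15 days into treatment. The last sample is "T2, second check, at 30th day since the begining of treatment: peripheral blood collection in view of verifying it" before that day's administration.

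Under Evaluation Parameters, the efficacy item is "Evaluation of oxidative stress biomarkers in the peripheral blood of the premature newborn before and after the treatment".

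The background text wants the markers assessed as "antioxidant potential (BPT) and total hydroperoxide (TH) during and after treatment". Under Duration of the period of administration, dosing starts within 36 hours of life and "continues with daily administration for 30 days".

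**The concern.** Three things are left open.

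1. **The role of T0.** A pre-treatment value of each marker is collected in both arms, and the named analysis does not use it. If T0 predicts T2, precision is given away in a trial of 50 infants.
2. **The deciding comparison.** T1 and T2 are equally eligible. A choice made after the code is opened could follow the data.
3. **The meaning of the before value.** The efficacy item implies a peripheral pre-treatment value, but the only pre-treatment sample is umbilical-vein blood. A reader could take the item to mean a T2 minus T0 change, which would subtract one specimen type from another. The mismatch rules out only a peripheral-to-peripheral change. The between-arm comparison at T1 or T2 is unaffected.

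**Working it through.** **Inputs (Sample size section).** TH: difference 50 Ucarr, SD 64.0. BAP: difference 500 μmol/L, SD 466. There are 25 infants per arm. Alpha is printed as 0.05% and read here as 0.05; two-sided testing is assumed because sidedness is not stated. The TH target power is 80%: "For the TH assume a decrease of 50 Ucarr which is approximately 30% of the" control value.

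**The plan's own figure.** Normal formula for TH: n per arm = 2 × (1.960 + 0.842)² × 64² / 50² = 25.7, so 26 per arm, within two infants of the stated total of 50. For BAP at 90% power: 2 × (1.960 + 1.282)² × 466² / 500² = 18.3, so 19 per arm, and 25 is more than enough.

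**Unadjusted t test at 25 per arm.** For TH the standard error is 64 × √(2/25) = 18.10 and 50/18.10 = 2.76. Power is 78.9% by the normal formula and 77.2% by the exact noncentral t with 48 df. BAP power by exact t is 96.1%. The TH figure is close to the stated 80%, and an SD of 61.8 would give 80.0%. There is no sample-size error here.

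**ANCOVA on T0.** Let ρ be the T0–T2 correlation. The documents give no value, so a range is shown. Power is from the noncentral t with 47 df and noncentrality (difference/SD) × √12.5 / √[(1 − ρ²)(1 + F/48)], averaged over F ~ F(1, 48). The F term is the cost of chance imbalance in T0. The 20% and 40% columns assume that share of cord values is missing and filled with the mean of both arms combined (simulation, 400,000 trials per setting).

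| Assumed ρ | TH, T0 complete | TH, 20% missing | TH, 40% missing | BAP, T0 complete |
|---|---|---|---|---|
| 0 | 76.3% | 76.4% | 76.3% | 95.7% |
| 0.15 | 77.3% | 77.1% | 76.8% | 96.0% |
| 0.2 | 78.0% | 77.6% | 77.3% | 96.3% |
| 0.3 | 80.1% | 79.3% | 78.4% | 97.1% |
| 0.4 | 83.2% | 81.7% | 80.2% | 98.0% |
| 0.5 | 87.1% | 84.8% | 82.5% | 98.9% |

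With complete T0, ANCOVA breaks even with the t test for TH at ρ of about 0.15. TH reaches 80% at ρ of about 0.30 (complete), 0.33 (20% missing) and 0.40 (40% missing). Type I error with mean filling was 0.049 to 0.051 at 0%, 20% and 40% missing.

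**Interval width.** The mean half-width of the 95% CI for TH is 36.2 Ucarr unadjusted. With ANCOVA it is 34.9 at ρ = 0.3 and 31.7 at ρ = 0.5 with complete T0, or 35.6 and 33.8 with 40% missing.

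**The change-score reading.** With equal SDs at T0 and T2 (assumed), the SD of T2 − T0 is 64 × √[2(1 − ρ)]. A t test on that change has TH power of 48% at ρ = 0, 63% at 0.3 and 77% at 0.5. Up to a correlation of 0.5 it does no better than the plain T2 comparison.

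**The open timepoint.** For one marker tested at 0.05 at both T1 and T2, the chance of at least one false positive is 1 − 0.95² = 9.75% if the tests are independent, and about 8% at an assumed T1–T2 correlation of 0.7.

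**The case against.** The strongest reply is that ANCOVA is a preference. The t test is valid, and the gain rests on a correlation that the documents do not supply. It could well be low, since T0 is cord blood at birth and T2 is peripheral blood 30 days into treatment. At ρ = 0.3 the TH gain is 80.1 − 77.2 = 2.9 points with complete T0 and 78.4 − 77.2 = 1.2 points with 40% missing. This stands, and it is why the gain is called modest and conditional.

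It can also be said that T0's role is unspecified rather than excluded, because a t test on change would fit the before-and-after wording. That is fair, but this reading is the weaker analysis over the range shown, which is a reason to state the method.

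The missing-cord rates are assumptions. The Procedures section expects cord blood from every infant. The exclusion criteria bar only "infants hospitalized after 36 hours of life", so later admissions without a cord sample are possible but not shown to be likely. Mean filling also does nothing for an infant with no T2 value.

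Finally, naming T2 leaves TH and BAP as two unranked tests. That is correct; it is a separate matter which this change does not settle. None of these replies touches the timepoint or the endpoint wording, which need fixing whatever the correlation.

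**Conclusion.** The point holds as a worthwhile improvement at low cost. The planned test is valid and the sample size is not in error. The available text names no role for T0 and no main timepoint, and its efficacy wording does not match the sampling schedule. Some passages were removed and the text is broken just before the Procedures section, so absence can be judged only on what is available.

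For TH, adjustment moves power from 77.2% to between 76.3% and 87.1% over assumed correlations of 0 to 0.5 with complete T0, and to between 76.3% and 82.5% with 40% of T0 missing. BAP changes little. Confidence in the size of the gain is medium, because it depends wholly on the unknown T0–T2 correlation. The case for fixing the timepoint and the wording does not depend on it.

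**What to change.** - **Analysis.** For each marker, replace the t test with ANCOVA of the peripheral T2 value on group and the infant's own T0 value. Report the adjusted mean difference with its 95% CI.
- **Timepoint.** Name T2 as the main timepoint, with T1 supportive and analysed the same way. T2 is proposed because it falls at the end of the 30-day administration. Whichever is chosen must be fixed before the code is opened.
- **Missing T0.** Fill a missing cord value with the mean of both arms combined, so that no infant is dropped for lack of T0.
- **Endpoint wording.** Restate the efficacy item as peripheral TH and BAP at T1 and T2, adjusted for the umbilical-vein value at T0.

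The cost is wording only: no extra infants or samples, and ANCOVA is available in SPSS, the package already named. The downside is about 1 point of TH power (76.3% against 77.2%) if T0 and T2 are uncorrelated, and little or no gain below a correlation of about 0.2. Missing cord samples shrink the gain.
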